5.1 Details regarding function and quality of life endpoints

The PRO-QOL will consist of a battery of previously validated HR-QOL and Symptom Inventory questionnaires ⁶⁰⁻⁶⁸. This includes: M.D. Anderson Dysphagia Inventory (MDADI), M.D. Anderson Symptom Inventory-Head and Neck (MDASI-HN), M.D. Anderson Symptom Inventory – Brain Tumor (MDASI-BT) for skull base only, Anterior Skull-Base Questionnaire (ASBQ) for skull base only, Brief Fatigue Inventory (BFI), EuroQol (EQ5D), Performance Status Scale For Head and Neck Cancer Patients (PSS-HN), Work Productivity and Activity Impairment Questionnaire: Specific Health Problem V2.0 (WPAI:SHP). These questionnaires will be performed in person by mail or by phone or by secure electronic methods. The research coordinator will notify the patient via telephone, email or via electronic notification 1-3 weeks after the questionnaire is sent to remind the patient and give them the option of performing the survey by other means. During patient follow-up period, HR-PRO will be assessed at the completion of reirradiation, and subsequently during follow up visits for all patients up to 24-months post reirradiation (Table 2).

Clinician-rated, fibrosis-related measures will be conducted according to the schedule in Table 1. Clinician-rated measures are standard, brief procedures incorporated into the supportive care visits of patients receiving radiotherapy for HNSCC at MD Anderson Cancer Center. In addition to these functional measures, patients may be eligible for dual consent for an imaging study with serial MRI (separately funded) to quantify soft tissue parameters that may serve as an objective and quantitative imaging marker of fibrosis. PRO and functional outcome schedules are harmonized.

Cervical Range of Motion (CROM): A goniometer will measure CROM (degrees) to assess active cervical

spine ROM. Five core CROM measures will be collected, including cervical extension, sagittal plane at rest, lateral flexion (left/right), coronal plane at rest, and lateral rotation (left/right). The primary CROM measure of interest is cervical extension. Cervical extension measures are highly reliable (ICC=.90). Average extension measures in healthy adults aged 60 to 69 range from 57 degrees in males (SD: 10.5) to 65 degrees in females (SD: 13.3). Cervical extension measures decrease by approximately 5 degrees for each decade of life.⁶⁸

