13.4 Secondary Endpoints

- The study secondary endpoints include: Overall response rate by RECIST or RECIST 1:1

- 1- year locoregional control (LRC), locoregional failure free survival (LFFS), distant metastasis (DM) and overall survival (OS) rates
- Acute and late toxicity accessed by the Common Terminology Criteria for Adverse Events (CTCAE)-5.0
- Fibrosis-related toxicities/functional outcomes
- Patient Reported Outcome (PRO) measures of symptoms using MD Anderson Symptom Inventory (MDASI).
- Volumetric tumor regression rate and MRI kinetic biomarkers after M7824 plus SBRT therapy
- Quality-Adjusted-Life-Years (QALY) between M7824 plus SBRT reirradiation and historic SBRT reirradiation control

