13.5 Sample Size

The statistical considerations for the Phase I/II design are described as follows:

This is a phase I/II, open label, single arm study to evaluate M7824 plus SBRT in patients with locoregional recurrent HNSCC after prior head and neck radiotherapy that are not good candidates for salvage surgery (Figure 1). Patients must have evaluable disease by RECIST or RECIST 1:1 and a performance status ECOG 0-2. Time elapsed from prior radiotherapy must be at least 6 months.

Sample Size

In the phase I portion, 8 patients will be enrolled to access safety and toxicity. The primary endpoint is dose-limiting toxicity (DLT) defined as M7824 related \geq grade 3 adverse event (AE) unresolved to \leq grade 1 in \leq 28 days, or incomplete SBRT. DLT window is from first M7824 dose (D0) until 14 days post SBRT (D28). More than 2 DLTs in 8 evaluable patients will be considered unacceptable.

In the phase II portion, the primary endpoint is PFS at 1 year. Based on the prior studies [unpublished data from MD Anderson], we assume that the one-year PFS of the standard treatment is 0.60. If the new treatment improves the one-year PFS to 0.80 or higher, it will be considered a clinically important improvement. A sample size of 21 patients (with 1.5-year additional follow-up after the last patient is enrolled) will allow us to observe an improvement in 1-year PFS from 0.60 to 0.80. This will enable the study 80% power to detect the specified difference in PFS. Power was calculated using a log-rank test with a one-sided type 1 error rate of 0.10 (EAST 5.4 and STPLAN version 4.5). Based on our estimated accrual rate of 2 patients per month, we expect enrollment to be completed in 11 months. The total study duration is 29 months.

DMI (Data Management Initiative) database

Clinical data capture called DMI (Data Management Initiative) and CORe will be the electronic database used for this study's electronic case report forms.

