13.6 Statistical Analysis

Summary statistics including mean, standard deviation, median, and range will be provided for continuous variables such as age, BMI, lab measurements, and scores from some HR-PRO measures of symptoms, and frequency count and percentage will be provided for categorical variables such as gender, response, toxicity type and severity.

To assess the primary endpoint (PFS), we will use the methods of Gooley et al.⁴⁴ to estimate the cumulative incidence of PFS “events”. A PFS event is defined as death or disease progression, including locoregional recurrence/progression or distant metastases. Time to PFS event is measured from treatment initiation until a recurrence, progression or occurrence or death, whichever occurs first.

Secondary endpoints include local-regional control, locoregional failure-free survival (LFFS), distant metastases (DM), DM free survival (DMFS) and overall survival (OS). Local failure is defined as failure (recurrence or progression) within the prescribed radiation field, including failure within 2 cm of the radiation field. Local control is defined as absence of local failure. LFFS is defined as alive and free of local recurrence or progression. Time to an LFFS event is measured from treatment initiation until local failure or death from any cause, whichever occurs first. Similarly, time to a DMFS event is measured from treatment initiation until distant metastases or death from any cause, whichever occurs first. Finally, OS is measured from treatment initiation until time to death from any cause.

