The student t-test or the Wilcoxon rank sum test will be used to compare continuous variables between patient groups. The chi-square test or the Fisher’s exact test will be applied to evaluate the association between two categorical variables. Logistic regression models will be used to evaluate the effects of the important patient clinical factors including treatment on PFS. The distribution of time-to-event endpoints will be estimated using the method of Kaplan and Meier. Comparison of time-to-event endpoints by important subgroups will be made using the log-rank test. Proportional hazards regression may be employed for multivariate analysis on time-to-event outcomes. PROs will be assessed at the completion of reirradiation, and subsequently every ± 3 -months until 24-months post reirradiation. Generalized linear models for the repeated measures analysis will be performed to assess the change in PROs overtime with important covariates including treatment in the models.

The Investigator is responsible for completing safety summary report, and submitting it to the IND Office Medical Affairs and Safety Group, for review and approval.

Lead in phase/phase I:

Toxicity summary will be submitted after the first eight evaluable patients’ complete 1 cycle of therapy.

Approval from IND office will be obtained before advancing to phase 2.

Phase II:

Toxicity summary will be submitted after first 3 evaluable patients’ complete 1 cycle of therapy and every 3 evaluable patients complete cycle 1 thereafter.

A copy of the cohort summary should be placed in the Investigator’s Regulatory Binder under “sponsor correspondence”.

13.7

Subject Identification and Privacy

A unique number will be assigned to each subject, immediately after informed consent has been obtained. This number will serve as the subject's identifier in the trial as well as in the clinical trial database. All subject data collected in the trial will be stored under the appropriate subject number. Only the Investigators will be able to link trial data to an individual subject via an identification list kept at the site. For each subject, original medical data will be accessible for the purposes of source data verification by the Monitor, audits and regulatory inspections, but patient confidentiality will be strictly maintained.

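### Read literally, section 13.6 tests associations with ordered grades without using their order, and it names no within-patient method for the clinician-rated fibrosis and function measures (low priority)

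*Combined protocol and SAP*

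**What the plan says.** **Endpoint.** Section 13.4 lists "Fibrosis-related toxicities/functional outcomes" as a secondary endpoint. Section 1.4 names HN-LEF, L-SIDS, DIGEST and cervical range of motion (CROM) as functional outcome measures under the exploratory objectives, and commits to correlating biomarkers with clinical outcomes and toxicity.

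**Measurement.** Table 1 and its footnote schedule the swallow study (scored by DIGEST), CROM and HN-LEF at baseline, 3-6 months and 18-24 months after radiotherapy. Section 5.1 adds: "The primary CROM measure of interest is cervical extension".

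**Design.** Section 13.5: "This is a phase I/II, open label, single arm study".

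**Analysis (13.6).**
- Description: "frequency count and percentage will be provided for categorical variables such as gender, response, toxicity type and severity".
- Association: the chi-square or Fisher's "exact test will be applied to evaluate the association between two categorical variables".
- Continuous variables: "The student t-test or the Wilcoxon rank sum test will be used to compare continuous variables between patient groups".
- Repeated measures: "Generalized linear models for the repeated measures analysis will be performed to assess the change in PROs overtime".

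Section 13.6 does not mention CROM, HN-LEF or DIGEST by name.

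**The concern.** CTCAE severity, HN-LEF and DIGEST are ordered grades. A chi-square or Fisher test on the grade table gives the same answer however the columns are arranged, so it spends its power on patterns of no interest. Toxicity severity is named as categorical and only one test is offered for categorical pairs, so an analyst following the text would use that test for the marker-toxicity associations promised in section 1.4.

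The second gap concerns change over time. With one arm, the comparison available inside the trial for function is each patient against their own baseline. The only model in 13.6 that makes this comparison is reserved for PROs. The clinician-rated measures have the same repeated structure but no stated method.

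Mitigating reirradiation fibrosis is one of the four reasons that section 2 gives for combining M7824 with SBRT. With about 21 patients, a real change or association is easily missed, and in an open-label trial a method chosen after the data are seen invites selective analysis.

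**Working it through.** **Is there a figure to reproduce?** No. The sample size in 13.5 (21 patients, 80% power, one-sided 0.10) concerns 1-year PFS. No hypothesis, alpha, effect size or power is given for fibrosis or function, so everything below rests on assumptions, with a two-sided 5% level throughout.

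**(a) Ordered grades against a two-group marker.** Assumed: 21 patients split 10/11; grades 0-4 distributed 15/25/30/25/5% in the reference group; a proportional-odds shift in the other. Simulation compared the rank-sum test with a permutation chi-square on the grade table. With no shift they rejected in 4.3% and 4.7% of trials, so the comparison is fair.

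| Odds ratio | Rank-sum | Chi-square on grade table | Gain (points) |
|---|---|---|---|
| 2 | 11% | 7% | 4 |
| 4 | 34% | 20% | 14 |
| 6 | 56% | 33% | 23 |
| 8 | 68% | 44% | 24 |

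An independent repeat at odds ratios 4 / 6 / 8 gave 36 / 55 / 67% against 19 / 31 / 45%, that is gains of 17, 24 and 22. With a different distribution (30/30/20/15/5%) and odds ratio 2, the figures were 12% against 7% at N=21 and 10% against 7% at N=16. The gain is therefore about 3-5 points at odds ratio 2 and about 15-25 at 4-8, with simulation error of 1 to 1.5 points.

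**(b) Change in cervical extension.** Inputs from section 5.1: SD 10.5 (men) and 13.3 (women), both from healthy adults aged 60-69, and 5 degrees, which is the stated decline per decade of age. None of these describes irradiated patients. Within-patient correlation ρ is assumed. Power comes from the noncentral t distribution:

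- unpaired: δ = 5 / (SD·√(2/n)), df = 2n − 2
- paired: δ = 5 / (SD·√(2(1−ρ)/n)), df = n − 1

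For n=21 and SD 10.5, unpaired δ = 5/(10.5 × 0.3086) = 1.54 and power is 32.5%. With ρ = 0.5, paired δ = 5/(10.5 × 0.2182) = 2.18 and power is 54.7%.

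| n=21 | Unpaired | ρ=0 | ρ=0.3 | ρ=0.5 | ρ=0.7 |
|---|---|---|---|---|---|
| SD 10.5 | 32.5% | 31.2% | 41.9% | 54.7% | 76.4% |
| SD 13.3 | 22.1% | 21.3% | 28.4% | 37.5% | 56.2% |

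At ρ = 0 pairing loses 32.5 − 31.2 = 1.3 or 22.1 − 21.3 = 0.8 points. At ρ = 0.5-0.7 the gain runs from 37.5 − 22.1 = 15.4 to 76.4 − 32.5 = 43.9 points. For a 2-degree change with SD 13.3 and ρ = 0.5, power moves only from 7.6% to 10.1%. If 14 patients are followed (SD 10.5), it moves from 23% to 38% or 57% at ρ = 0.5 or 0.7.

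**(c) Change in a grade from baseline.** Assumed: 30/30/20/15/5% distribution, n=21, shift of 0.6 SD. Signed-rank power is 50% (ρ = 0.3) or 70% (ρ = 0.6), against 41% or 40% for an unpaired rank-sum. With n=12 and a 0.3 SD shift, all of these are at or below about 8%.

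**The case against.** **No passage says that grades will be tested by chi-square or Fisher.** The sentence that lists severity is about counts and percentages, and the test sentence names no endpoint. This stands in part. The link is a literal reading of a default, not a stated decision, and describing grade frequencies in one arm loses no power. But 13.6 offers no other test for such variables, and section 1.4 promises correlation of biomarkers with toxicity.

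**No passage prescribes an unpaired baseline-to-follow-up test.** This stands. The t-test and rank-sum test are for comparisons between patient groups. A reader might infer that the plan treats a patient's two visits as independent samples, but the documents do not say so. The gap is an unnamed method, and the gains in (b) and (c) are measured against a comparator that the plan never states.

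**Much of the domain is already handled.** This also stands. MDADI and LSIDS-HN are patient-reported, and section 5.1 places PSS-HN in the PRO battery, so the repeated-measures model reaches them. Cervical extension is continuous, so grade order does not arise. Overall response rate is binary, and Fisher's test suits a responder comparison.

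**The endpoints are unpowered and partly exploratory.** True, and this sets the priority. It does not remove the case for naming the method in advance.

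**Conclusion.** Two modest gaps in 13.6 hold. Its default test for variables that it calls categorical ignores the order of toxicity grades. It also names no within-patient analysis for cervical extension, HN-LEF or DIGEST, although all three are repeated measures in a single-arm trial.

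The size is conditional. For grades (10 versus 11 patients, assumed distribution), the rank test gains about 3-5 points at odds ratio 2 and about 15-25 at 4-8. For a 5-degree change in extension (n=21, healthy-adult SDs), pairing ranges from a loss of about 1 point at correlation 0 to a gain of about 15-45 at 0.5-0.7, relative to an unpaired test that is not in the plan.

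A reader might infer that the whole fibrosis and function endpoint loses a definite, large amount of power. The documents do not support that: no test, contrast, alpha, effect size or evaluable number is given for it, and the patient-reported part is already modelled longitudinally. Priority is low.

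**What to change.** Make two changes in 13.6.

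1. *Ordered grades.* State that associations of CTCAE severity, HN-LEF and DIGEST grade with two groups use the Wilcoxon rank-sum test, and with ordered or continuous factors Spearman correlation or the Jonckheere-Terpstra test. Keep chi-square and Fisher for nominal and binary variables, including responder versus non-responder.
2. *Change over time.* Extend the repeated-measures sentence from PROs to PROs and clinician-rated functional measures. Use a mixed model for change in cervical extension from baseline to 3-6 and 18-24 months, reported with 95% confidence intervals. Use a paired Wilcoxon signed-rank test against baseline for HN-LEF and DIGEST. Keep the frequency tables, and report the number assessed at each visit.

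The cost is two sentences of wording and slightly more analysis work. No new data, visits or patients are needed, and the rank-sum test is already in 13.6 for continuous variables.

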13. STATISTICAL CONSIDERATIONS

13.1 Study Design and Study Endpoint Summary

This protocol will be performed at M.D. Anderson, with a safety lead-in study to evaluate the safety, tolerability and feasibility of SBRT plus M7824 prior to initiation of the phase 2. The primary outcome for this study is the progression free survival (PFS) rate.

This is a phase I/II, open label, single arm study to evaluate M7824 plus SBRT in patients with locoregional recurrent HNSCC after prior head and neck therapy that are not good candidates for salvage surgery (Figure 1). Patients must have evaluable disease by RECIST or RECIST 1:1 and a performance status ECOG 0-2. Time elapsed from prior radiotherapy must be at least 6 months.

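### Section 13.6 plans to estimate a treatment effect that a single-arm trial cannot give, and it commits to logistic regression for PFS while leaving proportional hazards optional

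*Combined protocol and SAP*

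**What the plan says.** **Design.** Section 13.1: "This is a phase I/II, open label, single arm study to evaluate M7824 plus SBRT". Section 13.5 repeats this, and Section 13.2 gives M7824 to all patients, starting two weeks before SBRT.

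**Models.** Section 13.6 commits to a logistic model for PFS: "Logistic regression models will be used to evaluate the effects of the important patient clinical factors including treatment on PFS". It also plans generalized linear models for repeated measures to describe change in PROs, "with important covariates including treatment in the models". The same section plans Kaplan-Meier estimates and log-rank tests by subgroup. Proportional hazards regression is mentioned only as something that may be used for multivariate work.

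**Endpoint.** Section 13.6 defines PFS as a time from treatment initiation to progression or death. Section 13.3 makes the 1-year rate the primary endpoint, and Section 7 calls it a landmark.

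**Size.** Section 13.5: "A sample size of 21 patients (with 1.5-year additional follow-up after the last patient is enrolled". The planning values are "we assume that the one-year PFS of the standard treatment is 0.60" and "If the new treatment improves the one-year PFS to 0.80 or higher, it will be considered a clinically important improvement". On the lead-in: "In the phase I portion, 8 patients will be enrolled to access safety and toxicity". The text does not say whether these 8 are among the 21.

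**Comparator.** A historic SBRT control is named for quality-adjusted life-years only (Sections 1.3 and 13.4).

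**The concern.** A model can estimate a treatment effect only if treatment varies among the patients in it. Here it does not, so both models promise a result that the trial's own data cannot supply. A later analyst would have to drop the term or bring in a comparison group that the plan never specified. If that group were chosen after the results were known, an unplanned historical comparison could be presented as a prespecified one.

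The choice of model for PFS is a separate matter. The committed method reduces a time-to-event endpoint to yes or no, without saying at what time or how to classify a patient whose status is unknown. The method that uses event times and handles censoring is only optional. With few events, the committed method can also fail to give a finite estimate, or give one too unstable to read as a prognostic finding.

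**Working it through.** **1. The plan's own figure.** The hazard ratio under exponential PFS is ln 0.80 / ln 0.60 = 0.437. With one-sided alpha 0.10 and 80% power against a fixed historical rate, the events needed are (1.282 + 0.842)² / (ln 0.437)² = 6.57.
- Dividing by the event probability at the alternative over the stated follow-up (0.353, step 3) gives 18.6, so 19 patients; power at 21 is 0.835.
- Dividing by the average 1-year event rate, (0.20 + 0.40)/2 = 0.30, gives 21.9, so 22 patients; power at 21 is 0.787.

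The 21 patients lie between these one-sample calculations. The sample size is not disputed here.

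**2. Estimability.** For 21 patients on one regimen, the intercept and treatment columns are identical. The two-column matrix has rank 1, so the data determine only the sum of the two coefficients. A larger sample does not change this. With the treatment column removed, the remaining coefficients are estimable in the ordinary way.

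**3. Expected PFS events, with no dropout.**

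By 1 year the count is N × (1 − PFS). Over full follow-up, with uniform accrual over a = 11/12 year and f = 1.5 years after last enrolment, the event probability is 1 − [exp(−λf) − exp(−λ(f + a))] / (λa), where λ = −ln(1-year PFS).
- PFS 0.80: λ = 0.223, probability 0.353.
- PFS 0.60: λ = 0.511, probability 0.629.

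| N | Events by 1 year (PFS 0.80 to 0.60) | Events over full follow-up |
|---|---|---|
| 21 | 21 × 0.20 = 4.2 to 21 × 0.40 = 8.4 | 21 × 0.353 = 7.4 to 21 × 0.629 = 13.2 |
| 29 (if the 8 are additional) | 29 × 0.20 = 5.8 to 29 × 0.40 = 11.6 | 29 × 0.353 = 10.2 to 29 × 0.629 = 18.2 |

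The stated 11 months at 2 patients per month fits 21 (21/2 = 10.5), not 29 (29/2 = 14.5). With a = 14.5/12 the probabilities become 0.373 and 0.653, and the last cell 10.8 to 18.9. Scheduled neck and chest scans end at 24 months (Table 1), so the full follow-up counts are slightly generous.

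**4. No finite odds ratio.** Take one binary factor with no true effect, N = 21, and 1-year event probability p. A group of size n has no events or all events with probability q(n) = (1 − p)ⁿ + pⁿ. The chance that at least one group does so is 1 − [1 − q(n₁)][1 − q(n₂)].
- p = 0.20, split 10/11: 1 − (1 − 0.107)(1 − 0.086) = 18%.
- p = 0.20, split 5/16: 1 − (1 − 0.328)(1 − 0.028) = 35%.
- p = 0.40: 1% and 9% for the same splits.

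**5. What proportional hazards would deliver.** For an evenly split binary factor, the standard error of the log hazard ratio is about 2/√d for d events. With 7.4 events it is 0.735, so the 95% limits lie a factor of exp(1.96 × 0.735) = 4.2 either side of the estimate. With 13.2 events it is 0.550 and the factor is 2.9. This uses the data better but is still imprecise, hence one factor at a time and a descriptive label.

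**The case against.** **Treatment may mean something that varies.** Section 6.1.3 allows a range of prescribed radiation doses and two delivery platforms, and M7824 exposure differs when patients stop early. A comparison with historic SBRT is planned for quality-adjusted life-years. This stands to the extent that the request must be to define or delete, not only to delete. It does not rescue the text, because Section 13.6 names no variable, dataset or method. M7824 exposure also depends on progression, since dosing ends at progression, so it could not enter a PFS model as a simple baseline factor.

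**Censoring matters little for a 1-year status.** This is largely right. With 1.5 years of follow-up after the last enrolment, no patient is administratively censored before 1 year. Section 8.1 keeps patients who stop treatment for reasons other than progression on scheduled tumour assessments, and Section 8.2 asks withdrawn patients to continue survival follow-up. A binary model for a 1-year status is a legitimate choice. What remains is the unstated time point, the missing rule for dropouts (no dropout rate is given) and the loss of timing and later events.

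**Censoring is handled elsewhere.** It is: Kaplan-Meier, log-rank and optional proportional hazards are all planned. The point concerns only the covariate analysis that the plan commits to.

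**A multi-factor logistic model is an inference.** The sentence speaks of several factors and of models in the plural, so single-factor models are possible. The fix makes that explicit.

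**Proportional hazards also suffers from sparse events.** True, as step 5 of the working shows. The gain is more events and proper handling of dropout, not precision.

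**Conclusion.** The point holds in a limited form. The treatment coefficient in the PFS and PRO models cannot be estimated from this trial, and the committed PFS covariate model is less suitable than the optional one. At N = 21, a 1-year binary outcome uses 4.2 to 8.4 expected events against about 7.4 to 13.2 over full follow-up. If the 8 lead-in patients are additional, the counts are 5.8 to 11.6 against 10.2 to 18.2. None of these supports a multi-factor model. These figures assume exponential PFS at the plan's two rates, uniform accrual over 11 months and no dropout.

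A reader might infer more than the documents support:
- *That the models cannot be fitted at all.* Only the treatment coefficient is lost, and software commonly drops the redundant column.
- *That the fitted models would yield a spurious treatment odds ratio.* A constant covariate yields none. The risk lies in an unspecified comparator added later.
- *That logistic regression mishandles many censored patients.* For a 1-year status only dropouts are affected, and their number is unknown.
- *That there will be only 4 to 8 events.* That holds for 21 patients at 1 year only.

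The primary PFS estimate, the sample size and the safety monitoring rules are not affected.

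**What to change.** In Section 13.6:

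1. Delete treatment from the list of factors in the logistic PFS model and from the covariates in the PRO model. If a historical-control comparison is meant, name the patient-level dataset, the endpoint and the method, including how differences between the groups are adjusted for. If a treatment-exposure variable is meant, name it and say how its dependence on time and progression is handled.
2. Make proportional hazards regression the covariate analysis of PFS: one prespecified factor at a time, penalised if a group has no events, reported with confidence intervals and labelled descriptive.
3. If a logistic model is kept as a supplement, state that the outcome is PFS status at 1 year and give the rule for patients without that status.
4. List the covariates of the PRO model. Visit and baseline score are natural candidates, but that choice is partly one of preference.
5. State whether the 8 lead-in patients are among the 21.

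The cost is SAP wording. No new patients, visits or data are needed unless a historical dataset is intended.
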